6.4.3. Permitted Concomitant Medications

Local or regional palliative cryotherapy or radiation, such as for bone pain or palliative surgery (non-antineoplastic intent), are permitted (provided the target lesion is not a site of measurable disease and is not indicative of disease progression). If extended field radiation therapy or palliative radiation to a focal site of measurable disease is deemed to be in the best interest of the patient following discussion between the Investigator and the Sponsor, the patient will be censored for the primary analysis of efficacy. Study therapy should be ceased a minimum of 2 days prior to administration of palliative treatment and may be resumed 7 days after the procedure or when the patient has recovered from the side effects of the procedure. Moreover, endocrine therapy for controlled prostate or breast cancer is permitted, if approved by the treating physician. Patients are allowed to receive COVID-19 vaccination while being on study.

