12.6. Criteria for Handling of Patient Data

The criteria for handling patient data will be provided in the SAP.

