12.7.3. Efficacy Analyses

12.7.3.1. Primary Endpoint Analyses

Part A: Phase 1 Dose Escalation

Not applicable.

Parts B and C: Phase 1 Dose Expansion and Phase 2

ORR per RECIST v1.1 by ICR will be summarized descriptively. ORR will be estimated and the 2-sided 95% confidence interval (CI) will be calculated using the Clopper–Pearson method.

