4.2. Populations for Analysis

The analysis populations in the study are defined in [Table 3](#).

Table 3: Definitions of Analysis Populations

Analysis Population	Definition
All Consenting Population	All patients who signed an informed consent form (ICF).
All Treated Population	All patients who received at least one dose of the study drug. This is the primary population for dosing, efficacy and safety analyses.
DLT Evaluable Population	All patients in the Dose Escalation, except backfill patients, who either experienced a DLT during the 1st cycle of treatment including PK lead-in period, or who completed the 1st cycle without experiencing a DLT and with at least 80% of planned study treatments administered. This is the specific population for DLT summarization.
PK Analysis Population	All patients who received at least one dose of study drug and have at least one post-dose TAS3351 and/or TAS-05-14317 plasma concentration measurement will be evaluated for PK; unless significant protocol

	deviations may have affected the data or if key dosing information is missing. This is the primary population for PK analysis.
PK/ECG Analysis Population	All patients who received at least one dose of study drug, have a baseline and at least one post-dose ECG value, and have time-matched plasma concentrations to at least one post-dose ECG value.
Pharmacodynamic/Biomarker Analysis Population	All patients in the All-Treated Population who have at least one evaluable baseline and one evaluable post-dose pharmacodynamic/biomarker datapoint for analyses.

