5.5. Efficacy Analyses

Unless otherwise specified, all efficacy analyses will be performed based on all treated population. The definition for confirmation and duration of overall response is presented in the protocol Appendix C.

The description of each efficacy endpoint is provided in [Table 4](#).

Table 4: Efficacy Endpoint Definitions

Endpoint	Definition
ORR	The proportion of patients experiencing a best overall response of PR or CR (per RECIST 1.1), based on IRC (and Investigator assessment). (investigator assessment only for part A)
DCR	The proportion of patients experiencing a best overall response of SD, PR, or CR (per RECIST 1.1), based on IRC (and Investigator assessment) (investigator assessment only for A)
DoR	For patients who demonstrated CR or PR as the best overall response, the time from the first documentation of response as CR or PR (per RECIST 1.1 based on IRC and Investigator assessment; investigator assessment only for part A to the first documentation of objective tumor progression or death due to any cause, whichever occurs first. If a patient does not progress or die following a response, then their DoR will use the PFS censoring time. - (Date of PD/death or censoring) – (date of first response of CR/PR(as BOR)) + 1.
PFS (All treated)	Time from date of first dose to the date of documentation of disease progression, or date of death, whichever occurs first - (Date of PD/death or censoring) – (date of first dose) + 1.
OS (All treated)	Measured from the date of first dose until the date of death due to any cause - (Date of death or censoring) – (date of first dose) + 1.

The best overall response (BOR) is determined once all the data for the patient, which are assessments obtained after study treatment discontinuation or starting a subsequent anti-cancer therapy, are known. The following best overall responses are defined based on the timepoint level response.

- Complete Response (CR): Required two timepoint assessments of CR, with the second at least 4 weeks after the initial CR. An intervening timepoint assessment of PR, SD, or PD will not be confirmed as CR.
- Partial Response (PR): Required a first assessment of PR and a second assessment of PR (or CR) at least 4 weeks after the initial PR. An intervening timepoint assessment of SD or PD will not be confirmed as PR.

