5.5.3. Duration of Response (DoR)

Both DoR by ICR and DoR by investigator will be performed. [Table 5](#) summarizes event and censoring rules for DoR.

Table 5: Event and Censoring Rules for DoR

Event/Censor	Decision	Date of event or censor to consider for analysis
Documented first disease progression	Event	Date of 1 st PD scan
Death without disease progression	Event	Date of Death
Patients who not known to have progressed or died at the time of data cut-off	Censor	Date of last evaluable tumor scan (non-NE)
Patient progresses or dies immediately after two or more consecutive missed visits	Censor	Date of last evaluable tumor assessment prior to the two missed visits (non-NE)

For missing data, i.e., patients who were lost to follow-up or who have withdrawn their consent without radiological progression or reached the time point of analysis without a known record of death or disease progression, the DoR will be censored at the date of last evaluable tumor scan.

Secondary Analysis in Part A & B – DoR by investigator

The following analyses will be performed.

- The Kaplan-Meier method will be used to estimate the median and percentile with the 2-sided 95% CI calculated using the Brookmeyer and Crowley method.
- Swimmer plot of treatment duration and response will be provided.

Secondary Analysis in Part B – DoR by ICR

The following analyses will be performed.

- The Kaplan-Meier method will be used to estimate the median and percentile with the 2-sided 95% CI calculated using the Brookmeyer and Crowley method.
- Swimmer plot of treatment duration and response will be provided.

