6. CHANGES IN PLANNED ANALYSIS

All analyses specified in this SAP are consistent with the study protocol (Protocol 10073010 Amendment 2 (07-July-2023)).

SAP Version	Major Updates	Rationale
1.0	Original	
2.0	
 Section 4.1: The definition of the study period was added for clarity for the analysis Section 5.5.1: Unconfirmed response was added Section 5.5.4: The Intracranial ORR analysis for Part A as assessed by investigator was added for clarity Section 5.5.5: The Intracranial DoR statistical method for Part A as assessed by investigator was added for clarity Section 5.6.1.1: Actual Dose intensity per cycle and relative dose intensity per cycle summaries were removed. Cumulative dose calculation was changed to the sum of the doses administered to a patient during the treatment period by removing the division by BSA. Such changes were fit for purposes. Section 5.6.1.2: The number and percentage of patients with at least one dose increase and reason for the dose increase were removed. The number of dose increases (1, 2, >2) was removed. Section 5.6.2.1: Summaries of death were corrected from deaths within (30(+3) days and deaths after 33 days to deaths within 30 days and deaths after 30 days, respectively. This approach is consistent with general practice. Section 5.6.2.2-5: The analysis was changed to by dosing cohorts by grade. Section 5.6.4: Amylase and lipase were added with amendment 2. . Section 5.6.6: Additional details of ECG data collection were added for ease of understanding analysis. Section 5.6.7: Additional details of time-matched QTcF versus plasma concentration analysis methodology were added for ease of understanding analysis. Section 5.7.2.4: The analysis of dose proportionality further specified that for a given parameter, a minimum of 3 values per dose level must be available for that dose level to be included in the power model. 	Added/updated based on protocol amendment 1 & 2, and provided further details to clarify the analysis and removed content that was not applicable

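### Protocol 6.4.3 censors irradiated patients in the primary efficacy analysis, but that analysis is a binary response rate and neither document says how such a patient counts

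*Protocol*

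**What the plan says.** - Protocol 6.4.3 (Permitted Concomitant Medications): after the two kinds of radiotherapy named above, "the patient will be censored for the primary analysis of efficacy". The section also provides for study therapy to resume afterwards, so an irradiated patient may go on being treated and scanned.
- Protocol 12.7.3.1 (Primary Endpoint Analyses), Parts B and C: "ORR per RECIST v1.1 by ICR will be summarized descriptively", with a two-sided 95% Clopper–Pearson interval. Part A has no primary efficacy analysis. SAP 5.5.1 adds a 90% interval for Part B.
- Protocol 12.6: "The criteria for handling patient data will be provided in the SAP".
- Protocol Table 17 and SAP Table 3 define the All Treated Population as everyone with at least one dose. The SAP adds: "This is the primary population for dosing, efficacy and safety analyses".
- SAP 5.5 fixes best overall response (BOR) once all of the patient's data, "which are assessments obtained after study treatment discontinuation or starting a subsequent anti-cancer therapy, are known". The sentence is garbled. As worded it includes later scans, and it does not mention radiotherapy.
- SAP Table 5 "summarizes event and censoring rules for DoR" and Table 6 does the same for PFS. Neither has a row for radiotherapy or new therapy.
- SAP 6: "All analyses specified in this SAP are consistent with the study protocol".
- SAP 1 limits the SAP to Parts A and B.

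**The concern.** Censoring belongs to time-to-event data. A patient in a proportion is a responder, a non-responder, or not in the denominator. The protocol uses the word for ORR without saying which of these it means and leaves data handling to the SAP. The SAP says nothing on the point, yet declares itself consistent with the protocol.

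The treatment of irradiated patients would then be decided during the analysis, possibly with responses already known. There is no formal hypothesis, but excluding a 25% ORR is the stated basis for the sample sizes of Parts B and C. Both design cases sit only just above that figure, so the handling of a single patient could decide how the result is described.

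**Working it through.** **1. What each reading does to a patient irradiated at a measurable site**

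| Reading | Response confirmed before radiotherapy | Never a confirmed response | Response first reached or confirmed after radiotherapy |
|---|---|---|---|
| Removed from the analysis | leaves numerator and denominator; ORR falls | leaves denominator; ORR rises | leaves both |
| Assessments stop at radiotherapy | responder | non-responder | non-responder |
| SAP as worded (All Treated, all scans) | responder | non-responder | responder |

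Removal contradicts the All Treated denominator. The other two readings differ only in the last column.

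**2. The plan's own figures**

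The exact lower limit for x responders of n at two-sided level α is the α/2 quantile of Beta(x, n − x + 1). The upper limit is the 1 − α/2 quantile of Beta(x + 1, n − x).

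- Part C, 35/100 at 95%: 25.73% to 45.18%. This reproduces the stated 25.7% to 45.2%. For 34/100 the lower limit is 24.82%, so 35 is the smallest count that excludes 25%.
- Part B, 9/20 at 90%: 25.87% to 65.31%. The printed 27.4% to 68.0% does not reproduce; it is the exact 90% interval for 9/19 (27.39% to 67.99%). The plan's statement that 9/20 excludes 25% at 90% still holds. For 8/20 the lower limit is 21.71%, so 9 is the smallest count.

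**3. Patients who respond only after radiotherapy**

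The number k of such patients is an assumption; the documents give none. Start from a result that just excludes 25% when all k are counted as responders. The lower limits are:

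| Part, level | k | Counted as responders | Removed | Kept as non-responders |
|---|---|---|---|---|
| B, 90% | 1 | 9/20: 25.87% | 8/19: 22.97% | 8/20: 21.71% |
| C, 95% | 1 | 35/100: 25.73% | 34/99: 25.09% | 34/100: 24.82% |
| C, 95% | 2 | 35/100: 25.73% | 33/98: 24.44% | 33/100: 23.92% |
| C, 95% | 5 | 35/100: 25.73% | 30/95: 22.42% | 30/100: 21.24% |

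One patient is enough to change whether 25% is excluded, in either part.

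**4. Direction under removal**

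- Removing one non-responder from 8/20 gives 8/19: ORR rises from 40.0% to 42.1%.
- Removing one responder from 9/20 also gives 8/19: ORR falls from 45.0% to 42.1%.
- In Part C, removing one non-responder turns 34/100 (24.82%) into 34/99 (25.09%), which crosses the benchmark.

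**5. Interval level**

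At the 95% level of Protocol 12.7.3.1, the lower limit for 9/20 is 23.06%, and that for 8/20 must lie below its 90% limit of 21.71%. Neither excludes 25%, so the Part B crossing exists only for the 90% interval.

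**The case against.** The strongest reply is that little is really open. The All Treated Population settles the denominator, so under the SAP nobody is dropped. An irradiated patient without a confirmed response is simply a non-responder, and one whose response was confirmed beforehand is rightly a responder. A response needs confirmation at least 4 weeks later, and the primary read is central. Protocol 5.4 already makes radiotherapy to the only followed site(s) a reason to stop study drug. The Site Imaging Manual, or the data-handling document cited in SAP 7.4, may hold a rule; neither was available.

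Most of this stands, and it limits the point. It leaves a protocol sentence that the SAP does not carry out, and the last column of the first table. Confirmation does not protect against a lesion that stays smaller after irradiation. The discontinuation item does not say how the patient is analysed. An imaging manual cannot make censoring meaningful for a proportion.

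Stronger readings are tempting, but the documents do not support them:

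- *Irradiated patients must be either dropped or counted as drug responders.* The first table shows other outcomes.
- *The bias is always upward.* Removing a responder lowers ORR. That irradiated patients are mostly failing treatment is a clinical inference that the documents do not state.
- *Removal alone could make Part B exclude 25%.* Taking 8/20 to 8/17 gives a 90% lower limit of 26.0%. This requires 3 of 20 patients irradiated, all non-responders and all removed, and at 95% the limit is 23.0%.
- *DoR and PFS must be censored at radiotherapy.* If patients are irradiated because they are doing badly, such censoring is informative and could lengthen the estimated medians.

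**Conclusion.** The point holds in a limited form. The protocol's rule is undefined for the primary endpoint of Parts B and C, conflicts with the All Treated denominator if read as removal, and is not implemented in the SAP. Under the SAP as worded, the patients at risk of being wrongly credited are those whose response is first reached or confirmed after irradiation. For Part C the supplied SAP gives no rule at all.

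One such patient is worth about 4 percentage points on the Part B 90% lower limit (25.87 − 21.71 = 4.16) and about 1 point on the Part C 95% lower limit (25.73 − 24.82 = 0.91). Either shift can cross 25%, but only when the result is at the margin. How often this would happen cannot be judged, because no irradiation rate is given. The direction of any bias under removal is also open. The contradiction itself depends on none of these assumptions and should be corrected before response data are reviewed.

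**What to change.** - **Protocol 6.4.3.** Replace the censoring clause with: *the patient remains in the ORR denominator; tumor assessments after such radiotherapy are not used for best overall response, and the patient is a non-responder unless a response was confirmed before it.*
- **SAP 5.5.** Put the same rule into the BOR definition for Part B, and rewrite the garbled sentence on which scans count.
- **Part C.** Put the same rule into its analysis plan, since the current SAP stops at Part B.
- **DoR and PFS.** State how such radiotherapy is treated in Tables 5 and 6. Add a sensitivity analysis with the alternative handling: censored at the last scan before radiotherapy, or not censored.
- **eCRF.** Make sure it records the irradiated site or field as well as the date. Protocol Table 12 lists the period and reason for concomitant therapy but not the site, and the rule cannot be applied without it.

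The cost is wording in the protocol and the analysis plans, one extra sensitivity output per endpoint, and possibly one eCRF field. Sample size, visits and patient management do not change.

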6.4.4. Supportive Care

Supportive treatment should be provided based on available institutional or local guidelines.

6.4.4.1. Hematologic Support

Hematologic support (blood transfusions, granulocyte colony-stimulating factor [G-CSF], erythropoietin-stimulating agents) may be administered as medically indicated, according to the institutional site standards or American Society of Clinical Oncology (ASCO) guidelines.^{23,24,25}

6.4.4.2. Gastrointestinal Toxicities

Prophylactic treatment for diarrhea (such as loperamide) is permitted during the study if clinically indicated according to the institutional or published guidelines.²⁶

In the event of diarrhea, antidiarrheal therapy should be initiated as early as possible if not already receiving such therapy (eg loperamide). Patients should also be encouraged to drink fluids (for example, 8 to 10 glasses of clear liquids per day). Dehydration and any associated electrolyte disturbances should be prevented or corrected at the onset.

For the management of nausea/vomiting, antiemetics may be administered as clinically indicated. Antiemetics which have the potential to prolong QTc, such as 5-HT₃ receptor antagonists (eg, ondansetron) should be avoided when possible. Suggested antiemetics for the treatment of nausea include diphenhydramine, prochlorperazine, lorazepam, and/or steroids. If nausea is not controlled by these agents, and if antiemetics such as metoclopramide need to be used, then there should be additional ECG monitoring per Investigator discretion. In addition, dehydration and any associated electrolyte disturbances should be prevented or corrected at onset of symptoms.

6.4.4.3. Interstitial Lung disease (ILD) / Pneumonitis

If new or worsening pulmonary symptoms (eg, dyspnea) occur or radiological abnormalities suggestive of interstitial lung disease is observed, a full diagnostic workup (including high-resolution CT (HRCT), blood and sputum culture, and hematological parameters) should be performed. It is strongly recommended to perform a full diagnostic workup in

order to exclude alternative causes such as lymphangitic carcinomatosis, infection, allergy, cardiogenic edema, or pulmonary hemorrhage. In the presence of confirmatory HRCT scans where other causes of respiratory symptoms have been excluded, a diagnosis of interstitial lung disease should be considered. Consult lung disease specialists as indicated and consider corticosteroid administration.

6.4.4. Amylase or Lipase Elevations

If amylase or lipase are $>3 \times \text{ULN}$, radiological imaging should be performed to evaluate the presence/absence of pancreatitis or other etiologies.

6.5. Lifestyle Considerations

6.5.1. Dietary

Patients will be prohibited from consuming herbal supplements and/or ingestion of foods and beverages known to be strong inducers or strong inhibitors of CYP3A. Furthermore, the consumption of grapefruit juice, grapefruit hybrids, pomegranates, starfruit, pomelos, Seville oranges, or juice products is prohibited during the study.

6.5.2. Sun Protection

A preclinical toxicity study using TAS3351 indicated a potential risk for phototoxicity. For this reason, it is recommended to advise patients to avoid prolonged exposure to natural sunlight, avoid artificial sunlight (eg, suntan bed), wear protective clothing, lip balm, and use broad-spectrum sunscreen with a high sun protection factor (SPF) ≥ 30 when outdoors.

6.6. Contraceptive Guidance

To participate in the study, patients of childbearing potential must adhere to the contraception requirements from the day of study medication initiation, throughout the study, and up to 6 months after the last dose of study treatment.

For WOCBP (for definition see Section 5.1), including female study patients and partners of male patients, highly effective contraception is required during the study, and for 6 months after the last dose of study medication.

Highly effective contraception is defined as follows:

- Combined (estrogen and progestogen containing) hormonal contraception associated with inhibition of ovulation with an oral, intravaginal or transdermal form
- Progestogen-only hormonal contraception associated with inhibition of ovulation with an oral, injectable, or implantable form
- Intrauterine device
- Intrauterine hormone-releasing system
- Bilateral tubal occlusion
- Vasectomized partner with documentation of the success of the vasectomy
- Complete abstinence from heterosexual intercourse (periodic abstinence is not a safe method)

Male patients, unless sterile (vasectomy with post-procedure semen analysis), with partners who are WOCBP should use a male condom in combination with at least one of the effective contraception methods during the study and for 3 months after the last dose of study drug.

Donation of sperm or ova is not allowed during the study and for 6 months after the last dose of TAS3351.

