2.2.1.12. Reproductive and Developmental Risks

No reproductive and developmental studies have been conducted with TAS3351. Pregnant women and breastfeeding women should not be included in studies with TAS3351. Both males and females of reproductive potential must agree to use effective birth control during the study prior to the first dose and for 6 months after the last dose of study treatment for females, and 3 months after the last dose of study treatment for males, (or longer) based on local requirements.

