10.4. Other Safety Information

10.4.1. Pregnancy

If a patient becomes pregnant while in the study, the study treatment must be immediately discontinued. Pregnancy information in a female patient (or, with consent, for the female partner of a male patient while on study and during contraceptive period after last administration of the study drug) should be reported within 24 hours from the time the investigator first becomes aware of a pregnancy or its outcome. This should be performed by completing a Pregnancy Form and e-mailing it to Sponsor's Pharmacovigilance department or designee.

New and/or corrected information regarding the pregnancy obtained after submitting the initial Pregnancy Form must be submitted an updated Pregnancy Form to the Sponsor's Pharmacovigilance department or designee. Pregnancies must be followed to outcome by the investigator, even after study completion.

If the outcome of the pregnancy is a stillbirth, congenital anomaly/birth defect, or a serious event in the mother, it should be reported as an SAE to the Sponsor's Pharmacovigilance department or designee. Live births will be followed up by the investigator up to one month or per local regulations/practice. Any information that may be associated with the study drug should be reported even after study completion.

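### Section 6.6 gives 6 months of post-treatment contraception for partners of male patients but 3 months for the men themselves, so partner-pregnancy reporting after the study can be read either way

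*Protocol*

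**What the plan says.** Four sections of the protocol bear on this. In Section 6.6 each period is counted from the last dose.

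- **Section 6.6, opening sentence.** It says that "patients of childbearing potential must adhere to the contraception requirements from the day of study medication initiation, throughout the study, and up to 6 months", with no split by sex.
- **Section 6.6, WOCBP sentence.** For WOCBP, "including female study patients and partners of male patients, highly effective contraception is required during the study, and for 6 months".
- **Section 6.6, male-patient sentence.** Men with WOCBP partners, unless sterile, "should use a male condom in combination with at least one of the effective contraception methods during the study and for 3 months".
- **Section 6.6, last sentence.** It sets a separate rule on gamete donation: "Donation of sperm or ova is not allowed during the study and for 6 months after the last dose of TAS3351".
- **Section 2.2.1.12.** After giving 6 months for females, it adds "and 3 months after the last dose of study treatment for males, (or longer) based on local requirements".
- **Section 5.1, inclusion criterion 11.** It has the same split: at least 6 months for females and at least 3 for males, with the same allowance for local rules.
- **Section 10.4.1.** Pregnancies in female partners are to be reported, with consent, "while on study and during contraceptive period after last administration of the study drug". No number of months is given.

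**The concern.** The WOCBP-partner sentence and the male-patient sentence in Section 6.6 govern the same couple. In months 4 to 6 after the last dose, the first still requires contraception. Under the second, the requirement for a condom and a second method has ended. A site that counsels from inclusion criterion 11 sees only the 3-month figure for a man and no mention of his partner's 6 months.

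What is at stake is patient and partner safety, and the completeness of pregnancy reporting. Section 2.2.1.10 reports testicular germ cell degeneration and atrophy of female reproductive organs in animals. Section 2.2.1.12 says that no reproductive or developmental studies have been done. The trial is first-in-human, so there are no earlier clinical data to fill the gap.

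**Working it through.** No statistical figure is involved, so the check is a comparison of the text.

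**Step 1: the period for the man himself.** Sections 2.2.1.12, 5.1 and the male-patient sentence of 6.6 all say 3 months. Wherever males are named for contraception, the figure is the same. The only contraception wording that could give a man 6 months is the opening sentence of 6.6, which is not split by sex and says up to 6 months.

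**Step 2: the period for his WOCBP partner.** The WOCBP sentence of 6.6 says 6 months and names partners of male patients. The male-patient sentence ties the condom to a second contraceptive method for 3 months, so it covers the couple's contraception too. The gap is 6 − 3 = 3 months.

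**Step 3: does the split by sex explain it?** No. The split in Sections 2.2.1.12 and 5.1 is by the sex of the patient. Section 6.6 places partners of male patients under the 6-month rule.

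**Step 4: do local requirements explain it?** No. The 6-month partner period is set by the protocol itself for all sites.

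**Step 5: who is covered?** The male-patient sentence exempts sterile men and applies only to men with WOCBP partners. The documents give no expected number of men, so no affected count can be derived.

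**Step 6: what happens to reporting?** The window in Section 10.4.1 has two parts: time on study, and the contraceptive period after the last dose. The second part can be read as 3 or 6 months. The first part limits how often that matters:

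- Section 4.6 runs the Study Period to the end of survival follow-up, that is, to death or study completion.
- Section 5.4 says that stopping treatment is not withdrawal from the study.
- Survival follow-up applies to Parts A2 and B (Table 1) and Part C (Table 2). At the planned sizes that is 20 + 40 + 100 = 160 patients, for whom months 4 to 6 normally fall within time on study on either reading.
- Table 1 gives Part A1 no survival follow-up. Part A1 is up to 40 of about 200 patients, or 40/200 = 20%. Only non-sterile men with WOCBP partners among them are concerned.
- Patients in any part who have left the study are in the same position as Part A1.

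**The case against.** The strongest reply is that the sentences can be read together. Criterion 11 sets a minimum for men, so a 6-month partner rule does not breach it. Section 6.6 could be layered: condom plus second method for 3 months, with the partner's own highly effective method continuing to 6. A couple who followed both would violate neither. This stands as far as it goes: the instructions are not mutually exclusive. But the protocol does not say that the obligations are layered, and what a man agrees to at inclusion still differs from what Section 6.6 asks of the couple in months 4 to 6. The layered reading also leaves open which period Section 10.4.1 means.

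A second reply is that reporting has backstops. Section 10.4.1 asks for information that may be associated with the drug even after study completion, and Section 5.5 requires notification of related serious events whenever the investigator learns of them. This also stands in part. Both depend on a judgement of association with the drug, whereas the pregnancy rule itself does not.

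A reader might infer four stronger points that the documents do not support:

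- **That the male patient's own period is contradictory.** It is 3 months wherever males are named.
- **That the donation ban proves the conflict.** Donation is a separate restriction, and its period may differ by intent.
- **That the reporting window is undefined.** It is defined by reference to a period with two readings, and it also includes time on study.
- **That every male patient is affected.** The rule covers only non-sterile men with WOCBP partners.

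Inconsistent counselling is a possibility and not an established fact, because the consent wording is not in the text available.

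**Conclusion.** The point holds as an inconsistency in the current protocol text. Non-sterile men with WOCBP partners can be counselled to end dates 3 months apart, depending on the sentence used. The contraceptive period in Section 10.4.1 can be read as 3 or 6 months, and in practice that matters mainly for Part A1 patients and for those who have left the study.

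This rests on two assumptions. Time on study in Section 10.4.1 is taken to mean the Study Period of Section 4.6. The study is taken to be still open at month 6 after the last dose, since survival follow-up ends at study completion. If either fails, the ambiguity reaches further into the other parts.

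It is a minor point. It changes no endpoint, estimate, error rate or sample size, but it bears on partner safety and is easily removed.

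**What to change.** Reconcile Sections 2.2.1.12, 5.1 and 6.6 so that the post-treatment periods for the male patient and for his WOCBP partner are consistent. If two different periods are intended, say that they are separate obligations and give both wherever either appears, including inclusion criterion 11. Split the opening sentence of Section 6.6 by sex or align it with the rest. State the post-treatment partner-pregnancy reporting window in Section 10.4.1 as a number of months.

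Which period applies is a decision for the sponsor and regulators and is not judged here. The cost is protocol wording, with a matching check of the consent form. No assessment, visit or analysis needs to change.
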